PROPOSAL SUMMARY

Host Organization: University Hospital Río Hortega

Project Title: Predicting overall survival in glioblastomas using radiomic features of intraoperative ultrasound. A proposal for the creation of an international database of brain tumor ultrasound images.

Type of study: Ambispective observational

Start date & Duration: 1/10/2021 – 30/03/2022

1. Lay Abstract

Predicting the survival of patients diagnosed with glioblastoma (GBM) is essential to guide surgical strategy and subsequent adjuvant therapies. Intraoperative ultrasound (ioUS) is a low-cost, versatile technique available in most neurosurgical departments. The images from ioUS contain biological information possibly correlated to the tumor's behavior, aggressiveness, and oncological outcomes. Today's advanced image processing techniques require a large amount of data. Therefore, we propose creating an international database aimed to share intraoperative ultrasound images of brain tumors. The acquired data must be processed to extract radiomic or texture characteristics from ioUS images. The rationale is that ultrasound images contain much more information than the human eye can process. Our main objective is to find a relationship between these imaging characteristics and overall survival (OS) in GBM. The predictive models elaborated from this imaging technique will complement those already based on other sources such as magnetic resonance imaging (MRI), genetic and molecular analysis, etc. Predicting survival using an intraoperative imaging technique affordable for most hospitals would greatly benefit the patients' management.

2. Scientific Summary

We plan to carry out a multicentre retrospective study of patients operated with GBM diagnosis between January 2018 and January 2020, in order to set the base for future prospective collection of patients. All cases with an ioUS study will be included. All patients must count with B-mode modality. After an pseudonymization process, the images will be uploaded to a private cloud server. Demographic, clinical, conventional radiological, and molecular variables (IDH, MGMT) will also be collected. OS will be defined as the time elapsed between the histopathological diagnosis and the patient's death. The acquired data must be processed to

obtain a series of radiomic markers to perform the study. A pre-processing stage will be necessary (noise cleaning, despeckling, intensity normalization, filtering) to calculate radiomics measurements (histogram, volumetric, shape, texture, etc.). In the previous stage, a very high number of radiological features per subject will be calculated. Because the number of features is much higher than the data set, to avoid the curse of dimensionality, it will be necessary to reduce their number using feature selection and extraction techniques (standard in pattern recognition and radiomics) that allow choosing those characteristics (or transformations of them) that have greater discriminating power. A predictive model of survival will then be elaborated based on the features selected.

3. Project Details

3.1 Background and Scientific Rationale:

GBM are the most common primary brain neoplasm. The survival of these patients is approximately 15 months despite continuous efforts to find more effective treatments. ioUS is a low-cost, versatile imaging technique available in most neurosurgical departments. These images contain biological information with potential application in surgical practice in addition to being a handy technique for image-guided brain tumor surgery. Advanced modalities, such as contrast-enhanced ultrasound (CEUS), intraoperative ultrasound elastography (IOUS-E), and navigated three-dimensional (3D) ultrasound, currently make it possible to exploit the full potential of this imaging technique to achieve maximal safe tumor resections.

On the other hand, advanced medical image analysis allows the development of predictive survival models using radiomic features. Even though ioUS image quality and resolution could be considered inferior compared to other imaging techniques, such as MRI, there is growing evidence that the ultrasound images contain biological information that can be set as a base to create models that allow classification tasks such as benignity versus malignancy. The ultrasound's capacity as a prognostic marker in response to adjuvant treatments in breast pathology has recently been evaluated. One possible explanation may lie in the fact that echogenicity in the B-mode could be associated with cellularity, which, on the other hand, is related to tumor aggressiveness.

In recent publications, we have explored intraoperative ultrasound's ability to differentiate primary malignant tumors from metastases using artificial intelligence. Besides, we have made the first descriptions about the extraction of brain tumors' ultrasound radiomic characteristics and their correlation with survival. The ultrasound's main limitation is the dependency on the

explorer and the variability between the parameters used in image acquisition among different centers. For this reason, image pre-processing is a fundamental step. In this project, we intend to use an ultrasound modality as a reference, the B-mode. Only by gathering a vast set of cases we would be able to test image harmonization techniques to allow the generalization and adoption of our predictive model in other centers. Also, the creation of an international and public database, the **Brain Tumor intraoperative UltraSound DataBase (BraTioUS-DB)**, will allow the development of additional research lines, since, in addition to B-mode images, other modalities such as elastography, CEUS, vascular studies, etc. will be incorporated prospectively. Furthermore, other histopathological tumor types could also be included.

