3.2 Hypotheses

Intraoperative ultrasound images in B-mode harbour tumor texture features correlated with overall survival in glioblastomas.

3.4 Objectives:

- To determine the relationship between the radiomic features of intraoperative ultrasound B-mode and overall survival in glioblastomas.
- Develop a predictive survival model using the texture features with the highest discriminatory power.
- Validate the model against an external dataset and compare it with currently available predictive models.
- Build a data set that allows exploring various image harmonization techniques that allow the reproducibility of our predictions.
- Establish an international cooperation network (**BraTioUS-DB**) whose objective will be to interchange ultrasound images and clinical data of patients operated on for a brain tumor prospectively from its creation and start-up.

4. Research Plan:

4.1 Study sample:

The cases that meet the inclusion criteria mentioned in the following section will be collected retrospectively to carry out the project's first phase. From January 2018 to January 2020, it is

estimated that each center can contribute with a minimum of 20 cases. Therefore, the total sample size for this phase of the study will be approximately 120 patients.

4.2 Selection of patients:

The inclusion criteria will be:

- Adult patients operated between January 2018 and January 2020 with a pathological diagnosis of WHO grade IV astrocytoma (Glioblastoma).
- Intraoperative ultrasound study that includes B-mode images

The exclusion criteria will be:

- Other histopathological diagnoses. Even though the international database will be established in such a way that other tumor types can be included prospectively.
- Artifacts in ultrasound images that make their analysis impossible
- Stereotactic biopsies.

4.3 Data collection (retrospective phase):

Each center will collect the details of the intraoperative acquisition technique of the ultrasound images. These data should include:

- Manufacturer of the ultrasound equipment,
- Type of probe: linear, curve.
- Footprint size
- Frequency range
- Modality. Essential B-mode, other modes optional.
- Acquisition before or after dural opening.
- Co-registered magnetic resonance images when possible (navigated ultrasound).
- Number of explorers who perform the ultrasound study.

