Of all the B-mode ultrasound images made by each patient, at least three slices will be selected in which the largest tumor diameter is appreciated, the peritumoral region, and healthy parenchyma, ideally in two planes perpendicular to each other.

After pseudonymizing the images, they will be uploaded from each center to a private cloud server with authentication to ensure data privacy. The computing platform will be Box (www.box.com), a leading company in storing and protecting data worldwide. The contents uploaded to the cloud will be protected with integrated controls, specific permissions and robust user authentication systems. Furthermore, each file will be encrypted with AES 256-bit encryption in various locations (FIPS 140-2 certified). The platform also complies with

regulations such as the General Data Protection Regulation (RGPD), the Law of Transfer and Liability of Health Insurance (HIPAA), the Federal Program for Risk Management and Authorizations (FedRAMP). Regarding security, Box Shield (a Box feature) works as a first-level security tool, highlighting, for example, the automatic detection of malware and the prevention of cyberattacks. The details of its characteristics can be consulted at: <https://www.box.com/es-419/shield>.

Along with the images, the demographic and clinical data of each patient will be recorded:

- Karnofsky Functional Rating Scale (KPS).
- Age
- Sex
- Adjuvant treatment received: chemotherapy/radiotherapy
- Percentage of resection of the enhancing tumor volume and non-enhancing peritumoral region. Based on this percentage, resections will be classified as: 100% complete resection (GTR); Subtotal resection > 90% (SBT) and Partial Resection <90% (PR).
- Immunohistochemical data included in the current WHO classification for pathological diagnoses of glial tumors. IDH, ATRX and MGMT mutation.

4.4 Data collection (prospective phase):

Once the international collaborative network has been consolidated and the online platforms have been enabled, glioblastomas and other tumor strains will begin to be collected prospectively.

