The inclusion criteria will be all patients undergoing surgical intervention with a pathological diagnosis of a primary brain tumor with an intraoperative ultrasound study. Ultrasound modalities will not be limited only to B-Mode, but also, depending on each center's availability, to other modalities such as strain-type elastography, shear-wave elastography, and post-contrast ultrasound (CEUS), Doppler and Microvascular modalities (i.e., eFlow, fineFlow, among others) and navigated ultrasound.

The clinical and demographic data will be the same as those detailed for the retrospective phase of the project.

The cases stored prospectively will be made available to the participating centers. Creating an extensive database of ultrasound of brain tumors will allow the development of new projects and lines of research in the future. For its use, each center may prepare proposals for the use of

the database that must be approved by the network members and, if required, also by the Ethics Committees of each participating institution.

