The transfer of data about human beings to the repository will only be considered when: informed consents, ethical approval and, where applicable, approval of local data protection authorities cover the purpose for which the data is intended to be used. Since this study involves patients diagnosed with glioblastomas, the cases have perished at the time of data collection. Therefore, the exemption of informed consent will be requested for the retrospective phase of the study (see Annex). On the contrary, for the prospective collection of cases, the informed consent model will be used (see Annex). All data to be transferred to the repository will be pseudonymized. The data owner/data provider will be responsible for the pseudonymization process and ensure that identifiable variables are not transferred to the repository.

7. Communication Plan for Dissemination:

This project's results will be disseminated through its publication in scientific journals and international conferences focused on neuroimaging, ultrasound, neurosurgery, and neuro-oncology.

8. Outputs: Impact, potential beneficiaries and added value:

The research work, aligned with one of the items of the Horizon 2020 program (Health, Demographic Change and Wellbeing) in addition to two of the United Nations Sustainable Development Goals (Health and well-being, 3; Industry, Innovation and Infrastructure, 9), has a great potential for impact, both at a scientific-technical level and a socio-economic level.

Concerning the scientific-technical, it is considered that the development of models for pre-processing, advanced analysis of ultrasound images that apply to commercial scanners and that, in turn, derive in descriptors that generate a large amount of useful information about the macro and microstructural properties of brain tumors, will lead to an increase in the use of advanced ultrasound techniques in clinical practice and will generate an increase in scientific research projects focused on these imaging technique. Furthermore, such models' implementation will substantially improve radiological care (diagnosis, early detection and treatment).

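### The protocol presumes every retrospective case has died and gives OS a value only at death, yet its own figures imply that roughly 4-24% of eligible patients are alive at data collection

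*Protocol*

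**What the plan says.** Section 2 gives the only definition of the outcome: "OS will be defined as the time elapsed between the histopathological diagnosis and the patient's death". It also says that "All cases with an ioUS study will be included".

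Section 4.2 admits "Adult patients operated between January 2018 and January 2020 with a pathological diagnosis of WHO grade IV astrocytoma (Glioblastoma"), provided there are B-mode images. Vital status is not among the inclusion or exclusion criteria.

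Section 6, in asking for exemption from informed consent in the retrospective phase, gives as its reason that "the cases have perished at the time of data collection".

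Section 4.3 introduces its list with "Along with the images, the demographic and clinical data of each patient will be recorded". The list covers KPS, age, sex, adjuvant treatment, extent of resection and molecular markers. It contains no vital status, date of death or date last known alive. Section 4.4 carries the list over to the prospective phase: "The clinical and demographic data will be the same as those detailed for the retrospective phase of the project".

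The study dates in the proposal summary are "1/10/2021 – 30/03/2022". Section 3.1 says: "The survival of these patients is approximately 15 months". Section 4.8 plans a predictive model of survival and names no time-to-event method.

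**The concern.** The OS definition is complete only if every included patient has died. Section 6 asserts this, but nothing in the eligibility criteria secures it, and the latest-operated patients have fewer than two years of potential follow-up when the study opens. A living patient is therefore eligible under sections 2 and 4.2, has no OS value under section 2, and should not exist according to section 6.

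The main objective is to relate image features to survival. If the premise in section 6 leads centres or analysts to work with deaths only, the sample is selected on the outcome. Patients who outlived their follow-up are removed, and more of them among the recently operated. Cross-validation cannot show this, and neither can an external centre that collects under the same definition, because the selection is common to the training and test data.

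**Working it through.** **Sample size as stated.** Section 4.1 expects at least 20 cases per centre. Section 5 lists five collaborating centres, and the host makes six: 6 × 20 = 120, which is the stated figure. The protocol has no power or event calculation to reproduce.

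**Potential follow-up.** From the start of January 2018 to 1 October 2021 is 45 months, and from the end of January 2020 it is 20 months. At 30 March 2022 these become 51 and 26 months. Histopathological diagnosis is taken to coincide with surgery.

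**Share expected alive.** Assume surgery dates uniform over the window and Weibull survival S(t) = exp(−(t/λ)^k). The protocol does not say whether 15 months is a median or a mean, so both are used:

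- median: λ = 15/(ln 2)^(1/k)
- mean: λ = 15/Γ(1 + 1/k)

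Share alive = [∫ S(t) dt from f0 to f1]/(f1 − f0), with f0 to f1 equal to 20-45 or 26-51 months.

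Worked case (k = 1, median, 1 October 2021): λ = 15/0.693 = 21.64, S(20) = 0.397, S(45) = 0.125. Share alive = 21.64 × (0.397 − 0.125)/25 = 0.235, and 120 × 0.235 = 28.

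| 15 months read as | Shape k | Alive of 120, 1 Oct 2021 | Alive of 120, 30 Mar 2022 |
|---|---|---|---|
| median | 1.0 | 28.2 (23.5%) | 21.4 (17.8%) |
| median | 1.3 | 20.4 (17.0%) | 13.0 (10.9%) |
| median | 1.6 | 14.4 (12.0%) | 7.3 (6.1%) |
| mean | 1.0 | 15.4 (12.8%) | 10.3 (8.6%) |
| mean | 1.3 | 12.6 (10.5%) | 7.1 (5.9%) |
| mean | 1.6 | 9.8 (8.2%) | 4.4 (3.7%) |

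No scenario gives zero. The loss is uneven: in the worked case 40% of patients operated at the end of January 2020 are alive at the October cut, against 12.5% of those operated at the start of January 2018.

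**Effect of a deaths-only analysis.** Survival times were simulated with 15 months as the median and a normally distributed feature unrelated to surgery date. A Cox model with living patients censored at the cut was compared with a Cox model on deaths only. The hazard ratios are assumptions, since the protocol gives none.

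| True HR per SD | Censored | Deaths only, Oct 2021 (k = 1.0 to 1.6) | Deaths only, Mar 2022 (k = 1.0 to 1.6) |
|---|---|---|---|
| 1.5 | 1.50 | 1.20 to 1.30 | 1.23 to 1.35 |
| 2.0 | 2.00 | 1.43 to 1.60 | 1.48 to 1.68 |

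With N = 120, k = 1 and a true HR of 1.3, power falls from about 70% to 17% at the October cut and from 71% to 24% at the March cut.

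With no feature effect, simulation over k = 1.0 to 1.6 puts median OS among the dead at 10.4 to 13.4 months (October) or 11.4 to 14.2 months (March), instead of 15. Of patients who survive beyond 24 months, 49-70% (October) or 27-54% (March) are missing.

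**Direction of the bias** (k = 1, October cut, N = 120):

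- Null feature unrelated to surgery date: HR 1.00, about 5% rejections. No bias.
- Null feature correlated 0.7 with follow-up length: HR 0.84 (34% rejections), or 1.18 (32%) with the opposite sign. Spurious association.
- True HR 1.3 with correlation −0.7: 1.33 on deaths only, 1.31 censored. No attenuation.
- Binary feature with HR 2.0 up to 12 months and 0.5 after: average HR 1.36 censored, 1.75 on deaths only. Exaggeration.

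**The case against.** Diagnosis to death is the ordinary short form of OS. A censoring rule, a data cut-off and the choice of model are commonly left to a statistical analysis plan, which may exist here. That is fair, and silence on censoring alone would not be a finding. What goes beyond silence is the statement in section 6 that the cases have died, which conflicts with the eligibility window and the 15-month figure.

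A reader might infer that the protocol excludes living patients. It does not say so. Section 2 includes all cases with an ultrasound study, and a centre could report a patient as alive. The bias above therefore belongs to a deaths-only analysis that the wording invites but does not prescribe.

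A reader might also infer that every feature-survival association is pulled toward no effect. The simulations contradict this: null features unrelated to surgery date are unaffected, and features tied to surgery date or with time-varying effects can move away from the null.

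The section 4.3 list is weaker evidence than it first appears. It also omits the diagnosis date and OS itself, so it may not show all the outcome data to be collected. It still gives no sign that a last-contact date will be requested, and a later plan cannot censor at a date nobody collected.

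The prospective phase adds little. Section 4.4 reuses the list, but the protocol specifies no OS analysis of those cases.

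**Conclusion.** The concern holds in conditional form. The premise that all retrospective cases have died is contradicted by the protocol's own eligibility window, study dates and survival figure: about 4-24% of 120 patients, roughly 4 to 28, would be alive at data collection. The range rests on uniform accrual, Weibull shape 1.0 to 1.6, either reading of 15 months, and a cut at the start or end of the study period. These patients are eligible and have no OS value.

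If they are left out, true proportional effects unrelated to surgery date are typically attenuated. With 15 months as the median, HR 2.0 per SD falls to about 1.4-1.7 and 1.5 to about 1.2-1.35. The smaller shares alive under the mean reading would give less bias. Predicted survival would be too short, and features linked to surgery date, for instance through a change of equipment, could become spuriously associated. Censoring living patients recovers the true hazard ratio in these simulations.

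**What to change.** - **Section 2:** define OS as time from histopathological diagnosis to death from any cause. State that patients not known to have died are included and censored at the date last known alive, with one common data cut-off for all centres.
- **Section 4.8:** state that the predictive model is a time-to-event model that accommodates censoring.
- **Section 4.3:** add vital status, date of death and date last known alive. Section 4.4 inherits these.
- **Section 6:** reconcile the statement that the cases have died with the eligibility window, since the request for exemption from consent rests on it.

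The cost is protocol wording and three fields on the data form. Centres must look up a last-contact date for living patients, and some observations become censored. This is best settled before centres upload their data, because adding the fields later would mean a second review of records at six sites.

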3.2 Hypotheses

Intraoperative ultrasound images in B-mode harbour tumor texture features correlated with overall survival in glioblastomas.

3.4 Objectives:

- To determine the relationship between the radiomic features of intraoperative ultrasound B-mode and overall survival in glioblastomas.
- Develop a predictive survival model using the texture features with the highest discriminatory power.
- Validate the model against an external dataset and compare it with currently available predictive models.
- Build a data set that allows exploring various image harmonization techniques that allow the reproducibility of our predictions.
- Establish an international cooperation network (**BraTioUS-DB**) whose objective will be to interchange ultrasound images and clinical data of patients operated on for a brain tumor prospectively from its creation and start-up.

4. Research Plan:

4.1 Study sample:

The cases that meet the inclusion criteria mentioned in the following section will be collected retrospectively to carry out the project's first phase. From January 2018 to January 2020, it is

estimated that each center can contribute with a minimum of 20 cases. Therefore, the total sample size for this phase of the study will be approximately 120 patients.

4.2 Selection of patients:

The inclusion criteria will be:

- Adult patients operated between January 2018 and January 2020 with a pathological diagnosis of WHO grade IV astrocytoma (Glioblastoma).
- Intraoperative ultrasound study that includes B-mode images

The exclusion criteria will be:

- Other histopathological diagnoses. Even though the international database will be established in such a way that other tumor types can be included prospectively.
- Artifacts in ultrasound images that make their analysis impossible
- Stereotactic biopsies.

4.3 Data collection (retrospective phase):

Each center will collect the details of the intraoperative acquisition technique of the ultrasound images. These data should include:

- Manufacturer of the ultrasound equipment,
- Type of probe: linear, curve.
- Footprint size
- Frequency range
- Modality. Essential B-mode, other modes optional.
- Acquisition before or after dural opening.
- Co-registered magnetic resonance images when possible (navigated ultrasound).
- Number of explorers who perform the ultrasound study.

Of all the B-mode ultrasound images made by each patient, at least three slices will be selected in which the largest tumor diameter is appreciated, the peritumoral region, and healthy parenchyma, ideally in two planes perpendicular to each other.

After pseudonymizing the images, they will be uploaded from each center to a private cloud server with authentication to ensure data privacy. The computing platform will be Box (www.box.com), a leading company in storing and protecting data worldwide. The contents uploaded to the cloud will be protected with integrated controls, specific permissions and robust user authentication systems. Furthermore, each file will be encrypted with AES 256-bit encryption in various locations (FIPS 140-2 certified). The platform also complies with

regulations such as the General Data Protection Regulation (RGPD), the Law of Transfer and Liability of Health Insurance (HIPAA), the Federal Program for Risk Management and Authorizations (FedRAMP). Regarding security, Box Shield (a Box feature) works as a first-level security tool, highlighting, for example, the automatic detection of malware and the prevention of cyberattacks. The details of its characteristics can be consulted at: <https://www.box.com/es-419/shield>.

Along with the images, the demographic and clinical data of each patient will be recorded:

- Karnofsky Functional Rating Scale (KPS).
- Age
- Sex
- Adjuvant treatment received: chemotherapy/radiotherapy
- Percentage of resection of the enhancing tumor volume and non-enhancing peritumoral region. Based on this percentage, resections will be classified as: 100% complete resection (GTR); Subtotal resection > 90% (SBT) and Partial Resection <90% (PR).
- Immunohistochemical data included in the current WHO classification for pathological diagnoses of glial tumors. IDH, ATRX and MGMT mutation.

4.4 Data collection (prospective phase):

Once the international collaborative network has been consolidated and the online platforms have been enabled, glioblastomas and other tumor strains will begin to be collected prospectively.

The inclusion criteria will be all patients undergoing surgical intervention with a pathological diagnosis of a primary brain tumor with an intraoperative ultrasound study. Ultrasound modalities will not be limited only to B-Mode, but also, depending on each center's availability, to other modalities such as strain-type elastography, shear-wave elastography, and post-contrast ultrasound (CEUS), Doppler and Microvascular modalities (i.e., eFlow, fineFlow, among others) and navigated ultrasound.

The clinical and demographic data will be the same as those detailed for the retrospective phase of the project.

The cases stored prospectively will be made available to the participating centers. Creating an extensive database of ultrasound of brain tumors will allow the development of new projects and lines of research in the future. For its use, each center may prepare proposals for the use of

the database that must be approved by the network members and, if required, also by the Ethics Committees of each participating institution.

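### The planned model uses imaging features alone, so the study can show association with survival but not whether intraoperative ultrasound adds to known prognostic factors

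*Protocol*

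**What the plan says.** - **Hypothesis (Protocol 3.2):** "Intraoperative ultrasound images in B-mode harbour tumor texture features correlated with overall survival in glioblastomas".
- **Objective 2 (3.4):** "Develop a predictive survival model using the texture features with the highest discriminatory power".
- **Objective 3 (3.4):** "Validate the model against an external dataset and compare it with currently available predictive models". No comparator model and no measure of comparison is named.
- **Lay Abstract (section 1):** "The predictive models elaborated from this imaging technique will complement those already based on other sources". MRI, genetic and molecular analysis are given as examples of those sources.
- **Scientific Summary (section 2):** "Demographic, clinical, conventional radiological, and molecular variables (IDH, MGMT) will also be collected", and then "A predictive model of survival will then be elaborated based on the features selected".
- **Data collection (4.3):** "the demographic and clinical data of each patient will be recorded". The list covers KPS, age, sex, adjuvant treatment, extent of resection, IDH, ATRX and MGMT. Co-registered MRI is collected only where possible.
- **Data analysis (4.8):** reduce the features, build a survival model on those selected, and evaluate that one model. The evaluation options are five- or ten-fold cross-validation, a random split, or one collaborating centre as external cohort. The clinical and molecular variables do not appear in this section.

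**The concern.** The protocol makes statements of three kinds, and the analysis section serves only the first fully.

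1. Imaging features are associated with survival. A model of imaging features can address this.
2. The model will be validated externally and compared with available models. Validation has a listed option in 4.8. The comparison has none.
3. The imaging model complements what other sources already give. This is a statement about added value. It needs a model with the known factors, set against the same model plus the imaging score.

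Setting the imaging model beside an existing model under objective 3 does not fill the third gap. It shows which model discriminates better alone. A score that carries new information can lose that comparison, and a score that merely tracks age, KPS or molecular status can look prognostic. The planned results would not tell these cases apart. Section 8 nevertheless foresees the model's information being used when new therapies are applied.

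**Working it through.** **The plan's own figure.** Section 4.1 says it is "estimated that each center can contribute with a minimum of 20 cases". The host plus the five collaborators listed in section 5 make six centres: 20 × 6 = 120, which matches the stated total. Section 6 says the retrospective cases have died, so there are about 120 events. One centre held out for external validation has about 20 patients.

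**Assumed inputs, not in the protocol.** One standardised clinical index *c* stands for the known factors, with HR 2 per SD. A standardised imaging score *r* has correlation ρ with *c* and its own hazard ratio θ. The hazard is proportional to exp(ln 2 · *c* + ln θ · *r*), with n = 120 and no censoring. The score is taken as known, which favours imaging because no feature selection is involved. Each cell has at least 1,000 runs. C is the proportion of patient pairs in which the higher score belongs to the earlier death.

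**Check 1: a score with no effect of its own (θ = 1).** Percentage of runs with a Cox test significant at two-sided 5%:

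| ρ with clinical index | Unadjusted | Adjusted for *c* |
|---|---|---|
| 0.1 | about 8–10% | 5–6% |
| 0.2 | about 21–22% | 5–6% |
| 0.3 | about 40–42% | 5–6% |
| 0.5 | about 82–83% | 5–6% |

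The protocol does not give ρ, so this is a range and not an estimate.

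**Check 2: imaging score against clinical index, each alone.**

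| Score | C imaging minus C clinical | Adjusted test rejects |
|---|---|---|
| Pure proxy, ρ = 0.7, θ = 1 | −0.055 | about 6% |
| Real effect, ρ = 0, θ = 1.5 | about −0.07 | 97–98% |
| Real effect, ρ = 0.3, θ = 1.5 | about −0.05 | 97–98% |

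The SD of the difference for the real score is about 0.04, so the proxy's −0.055 lies within its range. The score with a real effect beats the clinical index in only about 4–9% of runs.

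**Check 3: other assumed values.** With clinical log HR 0.7 per SD, a proxy with correlation 0.8 gives a mean C difference of −0.037. An independent score with log HR 0.53 gives −0.040. The nested likelihood-ratio test rejects in 4.7% and 99.9% of runs. The head-to-head differences are almost equal, and the answers on added value are opposite.

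**Check 4: one held-out centre.** With about 20 patients, the SD of the C difference is about 0.08–0.11. The 95% half-width is then 1.96 × 0.08 = 0.16 to 1.96 × 0.11 = 0.22, well above the differences in check 2.

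**The case against.** **Comparators are detail for a statistical analysis plan.** This stands. A SAP may exist and could name the models and the measure, so their absence from 4.8 is not an error by itself. What remains is in the protocol: the model is described by imaging features in 3.4, in 4.8 and in the Scientific Summary, while the abstract asserts complementarity.

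**The complement statement is lay wording, not an objective.** This also stands, and it lowers the weight of the point. It is a reason to soften the sentence if no analysis is added. It does not make the sentence testable as the plan stands.

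**A proxy score really is correlated with survival.** Correct. A reader might take the unadjusted percentages in check 1 as false-positive rates for the hypothesis. They are not, because 3.2 claims only correlation. They would mislead only as evidence of added information.

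**Objective 3 does not fix a head-to-head C-index.** True. A reader might also infer that the protocol excludes clinical terms from the model. It does not; it gives them no role. The point is only that a stand-alone comparison, if that is what is done, would not show added value.

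**The near-certain adjusted tests in check 2 suggest that the added analysis is well powered.** They do not show that. They treat the score as known. The Scientific Summary and 4.8 say there are far more features than patients, so a selected score will carry less information and the result may be inconclusive.

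**Conclusion.** The point holds in limited form, at minor to moderate weight. The main hypothesis remains answerable, and the validation half of objective 3 has a listed option. What the plan cannot show is whether ultrasound adds to factors already recorded, and a stand-alone comparison with an available model would not show it either.

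That the two questions differ follows from the structure of the comparison. The sizes rest on the assumed clinical HR of 2, the assumed correlations and a score taken as known. They illustrate that the contrast is the wrong one for added value. They do not predict this study's results or its power.

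**What to change.** **In 4.8,** add one secondary, exploratory analysis. Fit three models in the same patients and the same validation folds, with feature selection inside the training folds:

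1. a clinical-molecular model with age, KPS, sex, IDH and MGMT, and with extent of resection either included or its exclusion justified;
2. the radiomic model;
3. the combined model, with the clinical terms forced in.

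Report the HR of the out-of-fold radiomic score adjusted for the clinical terms, and the change in C-index with a 95% CI. State in advance that a null result is not evidence of no added value. Testing details can be left to the SAP.

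**In 3.4,** describe the comparison with currently available models as descriptive, and limit any MRI comparison to patients who have MRI data. The three models above do not replace that comparison, since none of them is an available published or MRI model.

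**Cost.** Text changes and extra analysis work; the clinical and molecular variables are already to be collected. The clinical terms take about five or six degrees of freedom at about 120 events (120 / 6 = 20 events per term). Some molecular data may be missing and must be handled within the training folds. The result may be inconclusive.

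**Cheaper alternative.** If the analysis is not added, soften the complement statement in the Lay Abstract and keep objective 3 descriptive.
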